### Description of EuroQol 5 Dimensions (EQ-5D):

The EQ-5D-5L and Proxy version 1 for proxy EQ 5D-5L will be utilized in this study. The EQ-5D-5L scale consists of 5 specific questions (regarding mobility [walking], self-care [washing and dressing], usual activities, pain/discomfort, and anxiety/depression) with 5 levels of responses to each of the 5 questions and 1 overall health rating (EQ VAS). EQ-5D-5L health states, defined by the EQ-5D-5L descriptive system (responses and questions), will be converted into a single index value (or utility score) using conversion matrix from the developer based on country specific value sets, which is stored in the excel file EQ-5D-5L\_Crosswalk\_Index\_Value\_Calculator and demonstrated by SAS syntax based on United States ([Appendix 13.3](#)). The index values, presented in country specific value sets, are a major feature of the EQ-5D instrument, facilitating the calculation of quality-adjusted life years (QALYs) that are used to inform economic evaluations of health care interventions. The EQ VAS scale is numbered from 0 (the worst health) to 100 (the best health).

## 5.8 Exploratory Analyses

Exploratory analyses may be conducted as appropriate. Any exploratory analyses that are performed will be appropriately titled/labeled as exploratory and will be clearly distinguished from planned analyses when results are reported in the Clinical Study Report.

## 6 INTERIM ANALYSES

This is a fixed design. There is no interim analysis of efficacy and no alpha spending before final analysis.

## 7 CHANGES IN THE PLANNED ANALYSES

Due to correspondence with the FDA during the study, the primary analyses for the non-EMA registrations were changed during the study to use MMRM for continuous efficacy data and GLMM for categorical efficacy data. The pre-planned analyses were kept for EMA registration, based on pre-study scientific advice from the EMA. The overall change was the ordering of importance of these analyses for each specific registration.

The co-primary analyses of MoCA and CIBIC-Plus will not be censored based on changes in the AChEI and non-AChEI restricted medications. This is based on review of blinded data which showed no improvement on efficacy after the use of this medication. As a sensitivity analysis, changes in AChEI restricted medications will be censored for MoCA and changes in either AChEI or non-AChEI restricted medications will be censored for CIBIC-Plus. The censoring differs based on the clinical interpretation that CIBIC-Plus measures aspects that could change with changes in the non-AChEI restricted medications.

## 8 DEFINITIONS AND CONVENTIONS FOR DATA HANDLING

### 8.1 Efficacy data handling

#### 8.1.1 Pre-randomization/Baseline Efficacy

Baseline for all efficacy endpoints is defined as the last pre-treatment assessment. Additional baseline or mean baseline based on the mean of all pre-randomization values at the Screening and Baseline assessment will be explored to assess the potential pre-randomization variability in MoCA.

#### 8.1.2 Treatment Duration for Efficacy Analyses

If additional data are collected other than scheduled visits, the additional data will be mapped to the closest scheduled visit if the data on this scheduled visit is missing.

A treatment visit is defined as occurring between the first dose and Early Discontinuation (ED) Visit (for early discontinuations) or Week 12 visit (for completers). A Post ED visit is defined as occurring after the ED Visit, more detail below.

To allow for the separate analyses where 1) all data is used and 2) only data up to and including ED visit is used, two analysis flags will be presented for efficacy analysis visits. Subjects who have a post ED visit and treatment visit in the same window will flag 1) the one closest to target date out of the two visits for all data, or 2) the treatment visit for data up to ED visit.

Windowing Period	Study Day Range (Relative to First Dose)	Week
Screening	$(-42) \leq \text{Day} \leq (-8)$	
Baseline	$(-7) \leq \text{Day} \leq (-1)$	
Analysis Baseline	-	a
Treatment	$1 \leq \text{Day} \leq 63$	6 (d)
Treatment	$64 \leq \text{Day} \leq 98$	12 (d)
Post ED	$1 \leq \text{Day} \leq 63$	6 (e)
Post ED	$64 \leq \text{Day} \leq 98$	12 (e)
End of Treatment (EOT)	-	b
Follow up	Follow up visit	c

- a: All pretreatment assessments are conducted during Screening/Baseline Periods before Day 1. The Analysis Baseline is the last non-missing value measured during pretreatment phase.
- b: For completer, EOT is the Week 12 visit. For early discontinuation, EOT is the Early Discontinuation (ED) visit. If the above visits are missing, then the last non-missing value collected not later than 7 days after the last dose will be used.
- c: If follow up visit is missing, there will be no imputed follow up visit. Unscheduled visits can be mapped to follow up for listings, but the CRF follow up visit will be used for analysis.
- d: For assessments with no Week 6 planned assessment, the window for the Week 12 assessment is  $1 \leq \text{Day} \leq 98$ . The data must be within in the date of first dose and date of ED visit (for early discontinuation subjects). For completers, date of last dose is irrelevant, window the visit based on study day range in above table.
- e: These subjects have been discontinued from treatment but continue the study untreated. They will be flagged as Post ED in the data listings and datasets. These Post ED visits must be after the early discontinuation visit date. For assessments with no Week 6 planned assessment, the window for the Week 12 assessment is  $1 \leq \text{Day} \leq 98$ . For the analysis flag based on all data, where subjects have both Week 6 and Week 6 Post ED, the visit closest to the target date will be used, the same is true for Week 12.

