### 5.3.5 Handling of Missing Data, Drop-outs, and Outliers

#### 5.3.5.1 Efficacy

For non-EMA registration, for primary and secondary efficacy endpoints, there will be no imputation of missing value. MMRM and GLMM will be used to analyze repeated measures of continuous and ordinal data, respectively.

For EMA registration, for co-primary efficacy endpoint MoCA and all continuous secondary efficacy endpoints, there will be no imputation of missing value at individual level. The statistical estimate will be calculated based on the mean imputation method proposed by Mehrotra et al (2017). For EMA registration, the missing co-primary efficacy endpoint CIBIC-Plus and ordinal secondary efficacy endpoint will be imputed using control-based pattern imputation at subject level (Yuan 2014).

The date of change in AChEIs stable dose during treatment period, Screening and 12 weeks prior to Screening will be used in the sensitivity analysis to determine the censoring time. In case the date of change in AChEIs stable dose is missing, the missing date will be imputed similarly to missing start date of concomitant medication but replacing the First Dose Date by Last Visit Date before the change in AChEIs stable dose as reference date in the imputation. Please refer to AChEIs Stable Dose CRF page to determine the last visit date before the change in AChEIs stable dose. Where non-AChEI restricted medications are changed during the treatment period, Screening and 4 weeks prior to Screening (12 weeks prior to Screening for memantine), the above method will be used similarly.

Post-ED data will be included in all the analyses.

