## **EMA Analyses**

### **Co-primary Analysis of Change from Baseline in the MoCA Total Score at 12 Weeks for EMA registration**

The change from baseline of MoCA total score for E2027 dose compared to placebo will be analyzed using the approach proposed by Mehrotra et al (2017) with slight modification based on reasons for missing data. The following is a list of the missing reasons and their missing mechanisms:

Data not observed because of dropouts (primary reason) due to AEs, lack of efficacy or any other intercurrent events related to treatment or study outcome will be considered as missing not at random (MNAR). Where there are other/secondary reasons for dropout that relate to a new drug being taken in response to an AE, this will also be counted as MNAR, even if the primary reasons for drop out may not be classed as not related to treatment or outcome. Where data are not done with the patient continuing study, the data will be considered MNAR where reasons for missingness are related to AEs, the subject is sleepy/drowsy, the subject is delirious, or the subject refused/declined (where refusal was not related to withdrawal of consent).

Data not observed because of dropouts due to intercurrent events definitely not related to treatment or outcome (eg, withdraw consent due to logistical problems) will be considered as missing at random (MAR). Where data are not done with the patient continuing study, the data will be considered MAR where reasons for missingness are not related to AEs, the

subject is sleepy/drowsy, the subject is delirious, or the subject refused/declined, except if the refusal was due to withdrawal of consent.

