#### 5.4.2 Secondary Efficacy Analyses

Table 5 Secondary Efficacy Analyses			
Score		Analysis for non-EMA Registration	Analysis for EMA Registration
CGIC-DLB	Secondary analysis	GLMM	Proportional odds model with control-based pattern imputation
	Additional secondary analysis	Proportional odds model with control-based pattern imputation	GLMM
CFI	Secondary analysis	MMRM	Control based mean imputation with Mehrotra
	Additional secondary analysis	Control based mean imputation with Mehrotra	MMRM

MMSE	Secondary analysis	ANCOVA and multiple imputation (MI) assuming MAR	ANCOVA and control-based pattern imputation
NPI	Secondary analysis	MMRM	Control based mean imputation with Mehrotra
	Additional secondary analysis	Control based mean imputation with Mehrotra	MMRM
MoCA	Additional secondary analysis	Control based mean imputation with Mehrotra	MMRM
CIBIC-Plus	Additional secondary analysis	Proportional odds model with control-based pattern imputation	GLMM

Table 5 details the analyses for the secondary endpoints. Further details are described below.

The CGIC-DLB scale will be analyzed as ordinal response data in a manner similar to the primary analysis of co-primary endpoint based on CIBIC-Plus, according to both methods for non-EMA and EMA registrations.

CFI is a continuous variable and will be analyzed in a manner similar to the primary analysis of co-primary endpoint based on MoCA, according to both methods for non-EMA and EMA registrations.

For the non-EMA registration, MMSE will be analyzed using ANCOVA with MI assuming MAR. For the EMA registration, MMSE will be analyzed using ANCOVA with control-based pattern imputation at subject level for missing data handling (Yang Yuan, Paper SAS270-2014, SAS Institute Inc.). The ANCOVA model will include corresponding baseline as a covariate, with treatment group and randomization stratification variables as factors.

NPI will be analyzed in a manner similar to the primary analysis of co-primary endpoint based on MoCA, according to both methods for EMA, and non-EMA registrations.

The details of calculating all efficacy endpoints are presented in Section 8.3 ALGORITHMS FOR EFFICACY PARAMETERS.

Additional secondary efficacy analyses will be performed with or without inclusion of efficacy data collected after treatment discontinuation:

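### SAP 8.1.2 lets an early-discontinuation MMSE taken before Day 64 stand as the Week 12 value, so the imputation in 5.4.2 passes over those subjects; 5.3.5.1 also contradicts that imputation

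*SAP*

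**What the plan says.** **Window (SAP 8.1.2).** The general table puts Days 1 to 63 in Week 6 and Days 64 to 98 in Week 12. Footnote d (treatment visits) and footnote e (post-ED visits) then say: "For assessments with no Week 6 planned assessment, the window for the Week 12 assessment is" Day 1 to 98. For a discontinuer the treatment period runs up to and includes the ED Visit. The opening sentence of 8.1.2 also moves extra data to the nearest scheduled visit when that visit has no data.

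**Choice between two values.** In the all-data analysis, "where subjects have both Week 6 and Week 6 Post ED, the visit closest to the target date will be used", and footnote e applies the same rule to Week 12. SAP 5.3.5.1 adds: "Post-ED data will be included in all the analyses".

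**Schedule (Protocol Table 6).** MMSE is taken at Screening, Week 12, Follow-Up (Day 112), the ED Visit and unscheduled visits. MoCA, CFI, NPI and CGIC-DLB also have a Week 6 assessment.

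**Method for MMSE (SAP 5.4.2).** The first rule reads: "For the non-EMA registration, MMSE will be analyzed using ANCOVA with MI assuming MAR". A different approach is set for the other registration: "For the EMA registration, MMSE will be analyzed using ANCOVA with control-based pattern imputation at subject level for missing data handling". Table 5 repeats both.

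**General missing-data rule (SAP 5.3.5.1).** "For non-EMA registration, for primary and secondary efficacy endpoints, there will be no imputation of missing value". For EMA, the rule for MoCA and "all continuous secondary efficacy endpoints, there will be no imputation of missing value at individual level". Neither sentence excepts MMSE.

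**The concern.** Change in MMSE at 12 weeks is a named secondary efficacy endpoint, and the SAP chose a missing-data method specifically for it. The wide window decides, before that method is reached, that certain subjects are not missing. A score from the first weeks can be labelled as the 12-week result, and the stated method then acts only on subjects with no MMSE anywhere in Days 1 to 98. For these subjects the ED score is in effect carried forward, a strategy that the SAP names nowhere for MMSE. The same person at the same visit is treated differently on MoCA, CFI and NPI.

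The second problem needs no assumption. A programmer cannot follow both 5.3.5.1 and 5.4.2 for MMSE. If the conflict is left open, the MMSE result depends on a choice made at programming.

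**Working it through.** **1. Which endpoint is caught.** By Table 6, MMSE is the only secondary efficacy scale with no Week 6 assessment, so footnotes d and e reach MMSE alone.

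**2. The rule applied case by case** (target Day 84, all-data analysis).

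| MMSE available | Week 12 value under footnotes d/e | Week 12 value with Day 64–98 |
|---|---|---|
| ED Day 14, nothing later | Day 14 score (84 − 14 = 70 days early) | missing, imputed |
| ED Day 35 or Day 63, nothing later | the ED score | missing, imputed |
| ED Day 14, Follow-Up Day 112 | Day 14 score (Day 112 is outside the window) | missing, imputed |
| ED Day 14, post-ED Day 84 | Day 84 score | Day 84 score |
| ED Day 70 | Day 70 score | Day 70 score |
| none in Days 1–98 | missing, imputed | missing, imputed |

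Only the first three rows differ. When data are restricted to the ED Visit and before, as in the second set of by-visit summaries in 8.1.3, an in-window ED score stands even for a subject who returns at Week 12.

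**3. The two missing-data sections side by side.**

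| Registration | 5.3.5.1 | 5.4.2 and Table 5, MMSE |
|---|---|---|
| non-EMA | no imputation for secondary endpoints | multiple imputation under MAR |
| EMA | none at individual level for continuous secondary endpoints | control-based imputation at subject level |

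**4. How many subjects.**
- The plan's own figure (SAP section 4): 80 / (1 − 0.12) = 90.9, so 91 per arm and 182 in total. It reproduces.
- Planned dropouts: 182 × 0.12 = 21.84, about 22.
- The share with an early ED MMSE and none in Days 64 to 98 is not given. At assumed shares of 0, 25, 50, 75 and 100%, the count is 0, 5.5, 10.9, 16.4 and 21.8.
- If ED days are uniform over Days 1 to 84, the share before Day 64 is 63/84 = 0.75, giving 16.4. This also assumes that every dropout has an ED MMSE and that none returns.

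**5. Is the direction fixed?** Set the completers' effect to 1. Assume 12% dropouts with none returning, ED days as above, and an effect that grows linearly to Day 84. The mean onset is 32/84 = 0.381 for EDs on Days 1 to 63 and 74/84 = 0.881 for Days 64 to 84. Imputed values carry no effect if MNAR and the full effect if MAR.

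Dropouts share the completers' effect:
- as written: 0.88 + 0.12 × (0.75 × 0.381 + 0.25 × 0.881) = 0.941
- Day 64–98, all MNAR: 0.88 + 0.12 × 0.25 × 0.881 = 0.906; ratio 1.038
- Day 64–98, all MAR: 0.906 + 0.12 × 0.75 = 0.996; ratio 0.944

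Dropouts have no effect:
- as written: 0.88
- Day 64–98, all MNAR: 0.88; ratio 1.000
- Day 64–98, all MAR: 0.97; ratio 0.907

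The ratio falls on either side of 1. The calculation shows only that the sign is open. It does not estimate the size.

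**The case against.** The strongest defence is that the window is a choice, not a slip. It is written out in two footnotes, it agrees with the opening mapping sentence of 8.1.2, and under that section the values are not missing, so nothing in 5.4.2 is broken. On the second part, 5.4.2 and Table 5 name MMSE and its method, while the sentence after the non-EMA rule in 5.3.5.1 speaks of repeated measures, which MMSE is not. The specific text would then override the general, and the conflict is editorial.

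Much of this stands. The window is deliberate, and the conflict can be cured by an edit. The count is also soft: the 12% is a rate of not completing the study, whereas subjects who stop drug are expected to keep attending visits, and those seen at Week 12 contribute their actual score. An ED MMSE would also be a poor imputation predictor. If nobody returns, no early discontinuer has both scores; if half do, placebo supplies about 91 × 0.12 × 0.75 × 0.5 = 4 subjects.

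One part does not stand. Being prespecified does not turn a Day 14 score into a 12-week measurement. It also does not explain why MMSE should be handled differently from MoCA, CFI and NPI at the same visit, or why a method chosen for MMSE should miss many of the subjects it was presumably meant for.

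A reader might go further and infer that the rule favours E2027. The documents do not support that. The direction depends on the drug effect in dropouts, its onset, the return rate and the MAR/MNAR mix. Subjects who leave for adverse events or lack of efficacy, whom the SAP's EMA analysis classes as MNAR, need not share the completers' effect.

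**Conclusion.** Both parts hold as a minor point. Footnotes d and e make an ED MMSE from before Day 64 the observed Week 12 value for any discontinuer with no MMSE in Days 64 to 98, including one whose only later MMSE is the Day 112 Follow-Up. Independently, 5.3.5.1 contradicts 5.4.2 and Table 5 for MMSE under both registrations.

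The reading of the text is firm. The count, 0 to about 22 with 16 as one scenario, rests on the 12% planning rate and the assumptions stated with it. No figure for the shift in the MMSE estimate can be drawn from the documents.

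Two further inferences should be resisted:
- The non-EMA shift is not shown to be an error. SAP 5.4.1 defines its effect of interest, for the co-primaries, irrespective of stopping treatment, and MAR imputation would itself credit these dropouts with close to the completers' effect.
- The co-primaries are not touched, since MoCA and CIBIC-Plus both have Week 6 assessments and keep the Day 64 to 98 window.

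**What to change.** **SAP 8.1.2.** In footnotes d and e, use Day 64 to 98 as the Week 12 window for MMSE. State that the opening mapping sentence does not move an earlier ED or unscheduled MMSE to Week 12; otherwise it could undo the change. Keep the early ED MMSE as the End of Treatment value under footnote b, and report the Day 1 to 98 version as a sensitivity analysis.

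**SAP 5.3.5.1.** Except MMSE from both sentences that rule out imputation, so that the section agrees with 5.4.2 and Table 5.

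**Imputation model.** Do not require the ED MMSE as a predictor. Week 6 MoCA may be listed as an optional auxiliary variable.

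**Cost.** Two footnotes, two sentences and a programming change. If about 16 more values are imputed, observed MMSE values fall from 182 to 182 − 16.4 = 165.6. With baseline as the only predictor, the confidence interval widens by a factor of about √(182/165.6) = 1.048, so up to about 5%. It widens less if some subjects return.

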### 8.1.3 Efficacy Data Collected After the ED Visit

Subjects who discontinue study drug are expected to continue in the study for the originally scheduled visits, starting with next such visit that is after the Early Discontinuation (ED) Visit. The scheduled visits post ED will be flagged to reflect its post ED status. The summary statistics by visit will presented twice, 1) for all data including those post ED, and 2) for data up to and including the ED visit.

### 8.1.4 Censoring of Efficacy Data Based on Changes in Medications

There are two types of censoring as part of the sensitivity analyses of the co-primary endpoints, censoring data based on changes to AChEI medications and censoring data based on changes in both AChEI and non-AChEI restricted medications.

MoCA AChEI only. CIBIC-Plus AChEI and non-AChEI restricted medications are censored. This is due to the type of effects measured by each set of scales and how the effects of changes in the groups of medications may affect these.

## 8.2 Safety data handling

### 8.2.1 Baseline Safety

The baseline value for all safety endpoints will be the last non-missing measurement occurring prior to the first dose of the study medication.

### 8.2.2 Treatment Duration for Safety Analyses

The treatment duration for all safety variables is considered to begin on Day 1 and ends 28 days after the last dose of study medication. Treatment emergent safety data (ie labs, vital signs and ECGs) are defined as observations that were recorded during treatment or within 28 days following the last dose of study drug, these will be flagged in the listings as “off treatment, but treatment emergent”. This data will be windowed and summarized as described below. Data after 28 days of last dose will be flagged as Post TE and listed only.

For summaries of safety by time points, the time points will be relative to date of first dose. For standardized reporting, study day windows relative to the first dose (Day 1) in the study will be applied to determine into which week the data will be mapped. All pretreatment assessments are conducted during Screening/Baseline Periods before Day 1. The Analysis Baseline is the last non-missing pretreatment assessments. Scheduled, unscheduled, and early discontinuation visits will be mapped to weeks. Table 8 below gives the mapping of relative day ranges to week for non-AE safety variables. If a subject did not have a recorded observation falling within a given range of days in order to be assigned to a week, the subject’s data for that week will be regarded as missing for summarization purposes. If there are two or more assessments in the same window, the following rules will be used:

- If the window is for the screening/baseline assessment, then the latest assessment will be used in the summary tables;
- If the window is for the follow-up assessment, then the latest assessment will be used in the summary tables;
- If the window is not for the screening/baseline or the follow-up assessment, then the assessment closest to the scheduled assessment will be used in the summary tables. Note that if two assessments are equidistant from the scheduled assessment then the last assessment of the two (within the allowable window) will be used.

Windowing Period	Study Day Range (Relative to First Dose)	Week
Screening	$(-42) \leq \text{Day} \leq (-8)$	
Baseline	$(-7) \leq \text{Day} \leq (-1)$	

Analysis Baseline	-	a
Treatment	$1 \leq \text{Day} \leq 21$	2
Treatment	$22 \leq \text{Day} \leq 35$	4
Treatment	$36 \leq \text{Day} \leq 53$	6
Treatment	$54 \leq \text{Day} \leq 74$	9
Treatment	$75 \leq \text{Day} \leq 98$	12
End of Treatment (EOT)	-	b
Follow up	Follow up visit	c

a: All pretreatment assessments are conducted during Screening/Baseline Periods before Day 1. The Analysis Baseline is the last non-missing value measured during pretreatment phase.

b: For completer, EOT is the Week 12 visit. For early discontinuation, EOT is the Early Discontinuation (ED) visit. If the above visits are missing, then the last non-missing value collected not later than 7 days after the last dose will be used.

c: If follow up visit is missing, there will be no imputed follow up visit.

For subject visits after the treatment emergent period (not defined as a CRF follow up visit) will be labelled as Post TE and listed only.

